**Dose Limiting Toxicity Definitions:**

The DLT evaluation interval begins on the first day of treatment upon start of infusion and continues for 21 days. Patients who receive at least 1 dose of study treatment and remain on study for the 21-day DLT evaluation interval or patients who discontinue study treatment for drug-related AEs before clearing the 21-day DLT evaluation interval will be considered evaluable for DLT determination.

DLTs during Phase 1a dose escalation are defined as any of the following deemed by the investigator as related to FPT155:

- Absolute neutrophil count (ANC)  $< 1.0 \times 10^9/L$  for  $> 5$  days duration or Grade 3 febrile neutropenia (eg, ANC  $< 1.0 \times 10^9/L$  with a single temperature of  $> 38.3^{\circ}C$  or fever  $> 38^{\circ}C$  for more than 1 hour)
- Platelets  $< 25 \times 10^9/L$  or platelets  $< 50 \times 10^9/L$  with clinically significant hemorrhage
- Aspartate aminotransferase (AST) or alanine aminotransferase (ALT)  $> 3 \times$  upper limit of normal (ULN) with concomitant total bilirubin  $> 2 \times$  ULN not related to liver involvement with cancer
- Grade 3-4 non-hematological toxicity except:
  - Grade 3 fatigue  $< 7$  days
  - Grade 3 nausea and Grade 3-4 vomiting and diarrhea lasting  $< 72$  hours in patients who have not received optimal anti-emetic and/or anti-diarrheal therapy
  - Grade 3 endocrinopathy that is adequately treated by hormone replacement
  - Laboratory value that may be corrected through replacement within 48 hours
- Grade 2 neurological toxicity except headache and peripheral neuropathy in patients with Grade 1-2 peripheral neuropathy at entry

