#### 4.1.1.3 Dose Limiting Toxicity Definitions

The DLT evaluation interval begins on the first day of treatment upon start of infusion and continues for 21 days. Patients who receive at least 1 dose of study treatment and remain on study for the 21-day DLT evaluation interval or patients who discontinue study treatment for drug-related AEs before clearing the 21-day DLT evaluation interval will be considered evaluable for DLT determination.

DLTs during Phase 1a dose escalation are defined as any of the following deemed by the investigator as related to FPT155:

- Absolute neutrophil count (ANC)  $< 1.0 \times 10^9/L$  for  $> 5$  days duration or Grade 3 febrile neutropenia (eg, ANC  $< 1.0 \times 10^9/L$  with a single temperature of  $> 38.3^{\circ}C$  or fever  $> 38^{\circ}C$  for more than 1 hour)
- Platelets  $< 25 \times 10^9/L$  or platelets  $< 50 \times 10^9/L$  with clinically significant hemorrhage
- Aspartate aminotransferase (AST) or ALT  $> 3 \times$  upper limit of normal (ULN) with concomitant total bilirubin  $> 2 \times$  ULN not related to liver involvement with cancer
- Grade 3-4 non-hematological toxicity except:
  - Grade 3 fatigue  $< 7$  days
  - Grade 3 nausea and Grade 3-4 vomiting and diarrhea lasting  $< 72$  hours in patients who have not received optimal anti-emetic and/or anti-diarrheal therapy
  - Grade 3 endocrinopathy that is adequately treated by hormone replacement
  - Laboratory value that may be corrected through replacement within 48 hours
- Grade 2 neurological toxicity except headache and peripheral neuropathy in patients with Grade 1-2 peripheral neuropathy at entry

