#### Additional DLT Considerations for FPT155 in combination with pembrolizumab

Because pembrolizumab is a known immune checkpoint inhibitor and one of the proposed mechanisms of action of FPT155 is immune checkpoint blockade, immune-related adverse events (irAEs) are anticipated with this combination. An irAE is defined as a clinically significant AE that is associated with study drug exposure, without a clear alternate cause, and consistent with an immune-mediated mechanism. Based on that background, the first occurrence of the following irAEs will not be considered a DLT because they may occur with immune therapy and are likely to be fully reversible per [Appendix 8](#):

- Grade 3 tumor flare (defined as local pain, irritation, or rash localized at sites of known or suspected tumor)
- Grade 3 non-skin immune-related adverse event (irAE) that resolve to a Grade 1 or less within 14 days with management per [Appendix 8](#)
- Transient (resolving within 6 hours of onset) Grade 3 infusion-related AEs
- Grade 3 drug-related bronchospasm or anaphylactic or anaphylactoid reactions

Dose escalation may be paused prior to determining an MTD based on observed safety, tolerability, or emerging PK or PD results.

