### 3. Recording an AE and/or SAE

AE and SAE Recording

The investigator will record all available relevant AE/SAE information in the CRF and send it to the sponsor or designee within 24 hours of becoming aware of the event.
 
There may be instances when copies of medical records for certain cases are requested by the Sponsor. In this case, all patient identifiers, with the exception of the patient number, will be redacted on the copies of the medical records before submission.
 
The investigator will attempt to establish a diagnosis of the event based on signs, symptoms, and/or other clinical information. Whenever possible, the diagnosis (not the individual signs/symptoms) will be documented as the AE/SAE.

Assessment of Intensity

Investigators need to assess the severity of AEs according to the guidelines provided in NCI-CTCAE, version 4.03. CTCAE v 4.03 Severity Grades are:
 
Grade 1: Mild; asymptomatic or mild symptoms; clinical or diagnostic observations only; intervention not indicated; mild AE
 
Grade 2: Moderate; minimal, local or non-invasive intervention indicated; limiting age-appropriate instrumental activities of daily living; moderate AE
 
Grade 3: Severe or medically significant but non-immediately life-threatening; hospitalization or prolongation of hospitalization indicated; disabling; limiting self-care activities of daily living; severe AE
 
Grade 4: Life-threatening consequences; urgent intervention indicated
 
Grade 5: Fatal AE
 
If the AE is not specified in the CTCAE or the study protocol, the grading of severity will be assessed as mild (Grade 1), moderate (Grade 2), severe (Grade 3), life-threatening (Grade 4), or death due to the AE (Grade 5) using the following definitions:
 
Mild: The patient is aware of the event or symptom, but the event or symptom is easily tolerated.
 
Moderate: The patient experiences sufficient discomfort to interfere with or reduce his or her usual level of activity.
 
Severe: Significant impairment of functioning; the patient is unable to carry out usual activities.
 
Very severe (life-threatening): The patient's life is at risk from the event.

Assessment of Causality

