## Haematological toxicities

Immune-related haematological AEs have rarely been described in patients treated with ICPi and do seem to occur. So far, lethal aplastic anaemia, autoimmune haemolytic anaemia and immune thrombocytopenic purpura have been described [82–84]. The optimal treatment of these often severe AEs is unknown. Initiation of high-dose corticosteroids and other immunosuppressive drugs should be carried out in close collaboration with a haematologist.

[figure not shown]

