6.3.1.3 Relationship of Adverse Event to Study Drug

A treatment related AE is an AE noted as related to FPT155 or pembrolizumab by the investigator. Events for which the investigator did not record relationship to study drug will be considered related to study drug for summary purposes. However, by-subject data listings will show the relationship as missing.

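### The DLT list names no fatal grade, so an FPT155-related death with no earlier qualifying stage is formally not a DLT and drops out of the Table 6 count, the MTD rule and the SAP DLT table

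*Protocol*

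**What the plan says.** Protocol 4.1.1.3 opens its definition with "DLTs during Phase 1a dose escalation are defined as any of the following deemed by the investigator as related to FPT155". Five items follow:

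- prolonged neutropenia or febrile neutropenia;
- low platelets;
- raised AST or ALT with raised bilirubin;
- "Grade 3-4 non-hematological toxicity except" four named situations;
- "Grade 2 neurological toxicity except headache and peripheral neuropathy in patients with Grade 1-2 peripheral neuropathy at entry".

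The synopsis and SAP 2.2.1 carry the same list. The combination text in 4.1.1.3 only removes events from it, for instance a first occurrence of "Grade 3 drug-related bronchospasm or anaphylactic or anaphylactoid reactions". Protocol 6.9.3 adds one route outside the list, a dose reduction needed during the DLT period.

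The grading scale in Protocol Appendix 2 has a separate line, "Grade 5: Fatal AE", and SAP 6.3.1.2 repeats it.

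On evaluability, 4.1.1.3 says that "patients who discontinue study treatment for drug-related AEs before clearing the 21-day DLT evaluation interval will be considered evaluable for DLT determination". Protocol 9.3 and SAP 4.3 instead require either 21 days on study or a DLT before then. Protocol 7.4 replaces escalation patients who are unevaluable for DLT and refers back to 4.1.1.3.

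**The concern.** Death is the most severe outcome the escalation rule could face, yet the general DLT item stops one grade short of it. The range is hard to read as shorthand for Grade 3 or worse, because these documents use open-ended wording where they mean it. Moderate AEs in Protocol 4.1.1.4 start at Grade 2 with no upper limit, and the SAP 6.3.1.6 tables use Grade 3 or higher.

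The DLT count carries weight. DLT incidence is part of the primary endpoints, and Table 6 is stated to apply to all escalation decisions. The MTD is defined by DLTs alone and caps the recommended dose (4.1.1.6). Combination escalation runs up to the monotherapy MTD (4.1.4). The rule still governs 840 mg, 1260 mg and the combination escalation of up to about 30 patients.

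**Working it through.** **The plan's own figures.** Protocol 4.5 gives a ceiling of 17% for treatment-limiting toxicity. The highest DLT count that still escalates is 1/6 = 16.7%, which rounds to 17%. The monotherapy escalation maximum of 58 is 4 titration levels × 1 + 9 levels × 6 = 4 + 54 = 58. Both figures reproduce.

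**Which related deaths already count.** A death is covered if the same event earlier met a listed item: a non-exempt Grade 3 or 4 non-haematological stage, a non-exempt Grade 2 neurological stage, or a qualifying neutrophil, platelet or AST/ALT-plus-bilirubin value.

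**What is left.** These are FPT155-related deaths with no such stage, for example:

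- a non-haematological event first recorded as Grade 5, such as a sudden or unwitnessed death;
- in combination cohorts, a first Grade 3 anaphylaxis or bronchospasm, which is exempt with no condition that it resolve, going to Grade 5 with no Grade 4 stage recorded;
- fatal anaemia or haemolysis without a qualifying neutrophil or platelet value and without a listed non-haematological stage. The guideline reproduced in Appendix 9 notes for checkpoint inhibitors that "lethal aplastic anaemia, autoimmune haemolytic anaemia and immune thrombocytopenic purpura have been described".

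**What happens to the patient.** There are two readings:

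- Under 4.1.1.3, if death from a related event is treated as stopping treatment for it, the patient is evaluable and has no DLT.
- Under Protocol 9.3 and SAP 4.3, the patient has neither 21 days on study nor a DLT, so is unevaluable. If that definition is applied, 7.4 has the patient replaced.

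**Table 6 outcomes.** The count is (listed DLTs + uncovered deaths) / n if the death is counted, and listed DLTs / n as the text stands.

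| Cohort | Death counted | Text, evaluable without DLT | Text, replaced |
|---|---|---|---|
| 3 patients, one such death | 1/3: enrol 3 more | 0/3: next level | 0/2 plus one replacement; 0/3 if clean: next level |
| 6 patients, one listed DLT and one such death | 2/6: stop, MTD is the level below | 1/6: next level | 1/5 plus one replacement; 1/6 if clean: next level |

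In the second row the observed rate is 2/6 = 33.3%, twice the 16.7% at which the rule still escalates. These are formal counts before any committee judgement. The documents give no rate for such deaths, so no probability is attached.

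**The case against.** The strongest reply is that the gap is small and well guarded. Appendix 2 describes Grade 4 as life-threatening, so most non-haematological deaths will have met a listed Grade 4 stage first. Escalation also rests on overall safety and on agreement by the Cohort Review Committee (4.1.1). A Grade 2 or higher related toxicity within 24 hours of completing the first dose holds enrolment. SAEs are reported within 24 hours (8.4.1). The recommended dose takes account of toxicities that are not DLTs (4.1.1.6). The SAP tabulates TEAEs leading to death and all deaths separately (6.3.1.6, 6.3.2), and AE and SAE incidence are themselves primary endpoints. The committee charter, which is not among the documents, may say more. All of this stands, and it limits the practical risk. None of it changes what the protocol and SAP define as a DLT.

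A reader might infer more than the text supports:

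- **That every related death is missed.** It is not; the earlier-stage routes cover many.
- **That the trial would escalate after a related death.** The committee provisions make that unlikely.
- **That completed levels were miscounted.** Protocol 2.3 reports no DLTs through 560 mg, and nothing shows that an uncovered death occurred.
- **That a death related only to pembrolizumab belongs to the same defect.** The lead-in requires relation to FPT155 for every item, fatal or not. This may be deliberate, since FPT155 is the drug being escalated and pembrolizumab is given at a fixed dose. SAP 6.3.1.3 is broader ("A treatment related AE is an AE noted as related to FPT155 or pembrolizumab"), but it defines related AEs for summaries and does not define DLTs. This is a separate design choice.
- **That fatal anaemia shows a gap specific to death.** It mostly reflects the absence of an anaemia item at any grade.

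The two evaluability definitions also differ where no death is involved. The point here is only what they do to a patient who dies.

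**Conclusion.** The point holds as a defect in the formal definition. An FPT155-related Grade 5 event with no earlier listed, non-exempt stage is not a DLT under the protocol or the SAP. It is therefore absent from the Table 6 count, the MTD rule and the table in SAP 6.3.1.7. In a cohort of three it turns 1/3 into 0/3; in a cohort of six with one listed DLT it turns 2/6 into 1/6. Each changes the formal decision.

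The conclusion rests on a literal reading of the list and on the two documents alone. The affected set is narrow, its frequency is unknown, and actual escalation after such a death is unlikely. The correction is recommended because the rule still governs open dose levels and costs little to repair.

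**What to change.** After the DLT list in the synopsis, Protocol 4.1.1.3 and SAP 2.2.1, add: *Any Grade 5 event within the 21-day DLT evaluation interval that the investigator judges related to FPT155 is a DLT; none of the exceptions in this section applies to it.* A separate sentence is safer than changing the general item to Grade 3 or higher, which would still miss a haematological death without a qualifying laboratory value.

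In the evaluability text of the synopsis and Protocol 4.1.1.3, and in Protocol 9.3 and SAP 4.3, add in identical words: *A patient with such an event is DLT-evaluable, is counted as having a DLT and is not replaced.*

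The cost is one sentence in three places and one in four, made through a protocol amendment with ethics approval and, where applicable, health-authority approval (10.1.2, 10.1.3), and a matching SAP update. No new visits or data are needed. If such a death occurs in a cohort of three, three more patients may be enrolled at that level. The monotherapy maximum of 58 already allows six at each 3+3 level.

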#### Additional DLT Considerations for FPT155 in combination with pembrolizumab

Because pembrolizumab is a known immune checkpoint inhibitor and one of the proposed mechanisms of action of FPT155 is immune checkpoint blockade, immune-related adverse events (irAEs) are anticipated with this combination. An irAE is defined as a clinically significant AE that is associated with study drug exposure, without a clear alternate cause, and consistent with an immune-mediated mechanism. Based on that background, the first occurrence of the following irAEs will not be considered a DLT because they may occur with immune therapy and are likely to be fully reversible per [Appendix 8](#):

- Grade 3 tumor flare (defined as local pain, irritation, or rash localized at sites of known or suspected tumor)
- Grade 3 non-skin immune-related adverse event (irAE) that resolve to a Grade 1 or less within 14 days with management per [Appendix 8](#)
- Transient (resolving within 6 hours of onset) Grade 3 infusion-related AEs
- Grade 3 drug-related bronchospasm or anaphylactic or anaphylactoid reactions

Dose escalation may be paused prior to determining an MTD based on observed safety, tolerability, or emerging PK or PD results.

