**FPT155+Pembrolizumab Dose Escalation:**

FPT155 will start at a dose level a minimum of 2 levels below that cleared in dose escalation with FPT155 monotherapy.

Pembrolizumab will be administered Q3 weeks at 200mg over 30 minutes on Day 1 of each 21-day cycle.

Dose escalation decisions will follow the standard 3+3 algorithm described above and continue up to the dose level established as the MTD for FPT155 monotherapy. Additional intermediate dose levels or dose regimens may be considered upon review of emerging safety, PK and PD results.

*Additional DLT Considerations for FPT155 in combination with pembrolizumab*

Because pembrolizumab is a known immune checkpoint inhibitor and one of the proposed mechanisms of action of FPT155 is immune checkpoint blockade, immune-related adverse events (irAEs) are anticipated with this combination. An irAE is defined as a clinically significant AE that is associated with study drug exposure, without a clear alternate cause, and consistent with an immune-mediated mechanism. Based on that background, the first occurrence of the following irAEs will not be considered a DLT because they may occur with immune therapy and are likely to be fully reversible per [Appendix 8](#):

- Grade 3 tumor flare (defined as local pain, irritation, or rash localized at sites of known or suspected tumor)
- Grade 3 non-skin immune-related adverse event (irAE) that resolve to a Grade 1 or less within 14 days with management per [Appendix 8](#)
- Transient (resolving within 6 hours of onset) Grade 3 infusion-related AEs
- Grade 3 drug-related bronchospasm or anaphylactic or anaphylactoid reactions

Dose escalation may be discontinued prior to determining an MTD based on observed safety, tolerability, or emerging PK or PD results.

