**Table 6: Algorithm for 3+3 Dose Escalation Decisions**

Number of Patients with DLT at a Given Dose Level	Dose Escalation Decision Rule
0/3 or 1/6	Enroll 3 patients at next dose level (next/higher cohort)
1/3	Enroll 3 additional patients at current dose level (current cohort)
$\geq 2$	Stop enrollment. If at the starting dose level, the study will be stopped. If at any other dose level, enroll 3 more patients at the previous dose level (previous/lower cohort) if only 3 were previously enrolled, or at an intermediate dose level

Abbreviations: DLT = dose limiting toxicity.

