**APPENDIX 8: ALGORITHMS FOR EARLY DETECTION AND TREATMENT OF IMMUNE RELATED ADVERSE EVENTS (IRAES)**

The guidelines provided below have been adapted from the European Society for Medical Oncology (ESMO) clinical practice guidelines for management of toxicities from immunotherapy (Haanen 2018). Please refer to the full publication for management of irAEs not specifically discussed below (Appendix 9). These may be supplemented by discussions with the sponsor's medical monitor as well as institutional guidelines on management of these toxicities.

Diarrhea and Colitis			
Grade	FPT155 Dosing	Management Escalation Pathway	Assessment and Investigations
Grade 1 Diarrhea : <4 stools/ day over baseline Colitis : asymptomatic	No delay or missed dose	Symptomatic management: Oral fluids, loperamide, avoid high fiber/lactose diet Persists >14 days or worsens, treat as Grade 2	Close monitoring for worsening symptoms Patient education to immediately report worsening symptoms
Grade 2 Diarrhea : 4-6 stools per day over baseline; Outpatient management if appropriate Colitis : abdominal pain, blood in stool	Delay or miss dose Reinitiate upon recovery to $\leq$ Grade 1	Symptomatic management: Oral fluids, loperamide, avoid high fiber/lactose diet Persists > 3 days or worsens 0.5-1.0 mg/kg (methyl)prednisolone or oral equivalent Persists >3 days or worsens, treat as Grade 3/4	Clinical safety labs (eg, CBC, chemistry, CRP) Stool microscopy for leukocytes/ova/parasites, culture, viral polymerase chain reaction (PCR), clostridium difficile toxin, cryptosporidia
Grade 3/4 Diarrhea (G3) : $\geq$ 7 stools per day over baseline; incontinence; requires hospitalization Colitis (G3) : severe abdominal pain, fever, ileus, peritoneal signs; medical intervention indicated G4 : Life-threatening, perforation	Permanently discontinue FPT155	1.0-2.0 mg/kg (methyl) prednisolone IV or IV equivalent Persists > 3 days, infliximab 5 mg/kg (if no contraindication)	Assess as above Urgent gastrointestinal (GI) consult and abdominal CT and/or sigmoid/colonoscopy

Hepatitis			
Grade	FPT155 Dosing	Management Escalation Pathway	Assessment and Investigations
Grade 1 AST or ALT > ULN-3.0 x ULN and/or T. bili > ULN-1.5 x ULN	No delay or missed dose	N/A	Close monitoring for worsening symptoms or laboratory parameters

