### General aspects of immune checkpoints blockade

#### Incidence and epidemiology

Immunotherapy with monoclonal antibodies (MoAbs) targeting cytotoxic T lymphocyte-associated antigen 4 (CTLA4) and the programmed death-1 receptor (PD-1) and its ligand PD-L1 has become standard of care for an increasing number of indications (Table 1). Therefore, an increasing number of patients will be exposed to these drugs with a chance of developing toxicities from these treatments. Depending on the immune checkpoint that is targeted, the incidence of toxicity varies. Toxicities from immune checkpoint inhibitors (ICPis) can be divided into infusion reactions and immune-related adverse events (irAEs) or adverse events of special interest (AEoSI). The latter will be the subject of these Clinical Practice Guidelines. Any organ or tissue can be involved, although some irAEs occur much more commonly than others. The most frequently occurring irAEs affect skin, colon, endocrine organs, liver and lungs. Others are very infrequent, but may be very serious, even lethal, such as neurological disorders and myocarditis.

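### Combination cohorts: read literally, the DLT rules count a Grade 2 neurological event but can exempt a Grade 3 neurological irAE that settles within 14 days

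*Protocol*

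**What the plan says.** The base DLT list in Protocol Section 4.1.1.3 covers FPT155-related events in Phase 1a dose escalation. It includes "Grade 2 neurological toxicity except headache and peripheral neuropathy in patients with Grade 1-2 peripheral neuropathy at entry", with no test of duration or reversibility. Grade 3 neurological toxicity is caught separately, under the general Grade 3-4 non-hematological item.

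For the combination, the Synopsis and Section 4.1.1.3 add that "the first occurrence of the following irAEs will not be considered a DLT". The list has four entries, all for Grade 3 events. One is a "Grade 3 non-skin immune-related adverse event (irAE) that resolve to a Grade 1 or less within 14 days", with management under Appendix 8. The reason given is that events are exempted "because they may occur with immune therapy and are likely to be fully reversible per" Appendix 8.

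Appendix 8 has tables for diarrhea and colitis, hepatitis, renal events, pneumonitis and skin, and guidance on endocrinopathy. It has nothing on neurological events. For what it leaves out, it says "Please refer to the full publication for management of irAEs not specifically discussed below", meaning the guideline reproduced in Appendix 9. That guideline says of the less common irAEs: "Others are very infrequent, but may be very serious, even lethal, such as neurological disorders and myocarditis".

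Section 4.1.4 applies the 3+3 algorithm to the combination. In Table 6, 0/3 leads to the next dose level, 1/3 adds three patients, and two or more DLTs lead to "Stop enrollment. If at the starting dose level, the study will be stopped". DLT incidence is a primary endpoint of the combination part (Protocol Section 3.0; SAP Section 3.3).

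**The concern.** A DLT rule should not become more lenient as the same kind of toxicity gets worse. The base list singles out neurological toxicity for a lower threshold than other organs, Grade 2 instead of Grade 3, and so treats it as of special concern. The combination exemption then waives short-lived Grade 3 events in every organ except skin, while the Grade 2 neurological item stays in force. On its face, a Grade 2 neurological event counts and a Grade 3 one that settles within 14 days does not.

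The monotherapy part has no such inversion, because Grade 3 neurological events count there under the general item. It arises only from the added exemption, which suggests a drafting oversight. The stated reason, likely reversibility under Appendix 8, does not fit an organ system that Appendix 8 does not cover.

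Two things are at stake in the combination cohorts: the count that feeds Table 6, and the DLT incidence reported as a primary endpoint.

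**Working it through.** **Inputs.** The DLT items and the exemption are from Protocol Section 4.1.1.3, the decision rule is from Table 6, and its use for the combination is from Section 4.1.4. The 21-day window is from Section 4.1.1.3. Neurological incidence and onset are from Appendix 9, Neurological toxicity.

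**The plan's own figure.** Table 6 allows escalation at 1/6. That is 16.7%, which agrees with the 17% standard in Section 4.5.

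**Counts in a cohort of three, no other DLTs.** Each event is in a different patient, is related to FPT155 and is not one of the two exceptions. Each Grade 3 event is an irAE that settles to Grade 1 or lower within 14 days. The exemption is taken to apply.

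| Events | Grade 2 | Grade 3, first occurrence per patient | Grade 3, first occurrence per cohort |
|---|---|---|---|
| One | 1/3, enroll three more | 0/3, escalation permitted | 0/3, escalation permitted |
| Two | 2/3, stop | 0/3, escalation permitted | 1/3, enroll three more |

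The protocol does not say whether first occurrence is per patient or per cohort. On both readings the Grade 3 result is more lenient than the Grade 2 result. If the Grade 3 events do not settle within 14 days, or if the exemption is not applied, two of them give 2/3 and stop.

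**How often.** The documents give no in-window rate for this combination. Appendix 9 reports neurological events in 1% of patients, and in an analysis of 59 trials 3.8% with anti-CTLA4, 6.1% with anti-PD-1 and 12% with both. These rates are for other drugs, with no split by grade. For illustration only, let p be one of those rates:

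- At least one event in three patients, 1 - (1 - p)^3: 3.0% at 1%, 17.2% at 6.1%, 31.9% at 12%.
- At least two, p^2(3 - 2p): 0.03% at 1%, 1.1% at 6.1%, 4.0% at 12%.

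These take every reported event as relevant. To matter here an event must also be Grade 3, start within 21 days and settle within 14. Appendix 9 puts onset at 6 to 13 weeks, and 6 x 7 = 42 days, twice the window. If that timing held for FPT155 with pembrolizumab, almost none would count.

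**Secondary case, the liver.** AST or ALT above 3 x ULN with total bilirubin above 2 x ULN is a DLT. Appendix 8 grades AST or ALT above 5 x ULN as Grade 3/4. A patient with enzymes between 3 and 5 x ULN and bilirubin above 2 x ULN counts. On one reading, a patient with the same bilirubin and enzymes above 5 x ULN, graded 3 and settling within 14 days, might be exempt.

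**The case against.** **The exemption may not reach neurological events.** It requires management under Appendix 8, which has no neurological algorithm. A reader might infer that the protocol firmly adopts an inverted rule; the documents do not support that. The redirection to Appendix 9 makes the exemption arguable for neurological events, not plain.

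**A narrower reading removes the inversion.** All four exemptions concern Grade 3 events, so they may be meant to waive only the general Grade 3-4 item and leave the neurological item standing. This is a fair reading, but the text does not state it. The neurological item also names Grade 2, not Grade 2 or higher, so those words have to be supplied.

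**Escalation is not automatic.** A reader might take 0/3 as forcing the next dose. It does not. Section 4.1.1 bases decisions on overall safety as well as DLTs, with committee agreement (the sentence sits under a monotherapy heading but speaks of all decisions). Section 4.1.1.3 lets combination escalation be paused on safety grounds, and Section 4.1.1.6 looks beyond DLTs for the recommended dose. Two Grade 3 neurological events would be before the committee whatever their label. This limits the consequence, but it does not correct the count reported as a primary endpoint.

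**The events are unlikely in the window.** This stands as the best available expectation. It is not certain: Section 6.9.4 warns that timing may differ from anti-CTLA-4 drugs, and Appendix 9 notes that irAEs may come earlier with combined blockade.

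**The SAP.** Its only DLT list, in SAP Section 2.2.1, has none of the four exemptions. A reader might infer that the combination DLT table will disagree with the counts used for escalation. The documents do not support that: the list sits in a design summary under a monotherapy heading, SAP Section 6.3.1.7 gives no rule for re-deriving DLTs, and SAP Section 1 ties the plan to protocol Amendment 4, which contains the exemptions.

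**Conclusion.** The point holds as an ambiguity that, on the literal reading, inverts severity. Where the exemption applies, the more severe neurological event always gives the more lenient count: 0/3 against 1/3 for one event, and 0/3 (per patient) or 1/3 (per cohort) against 2/3 for two. This rests on reading the redirection to Appendix 9 as satisfying the management condition, and on the exemption overriding the whole base list and not only the general Grade 3-4 item.

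The practical effect is probably small, given the 21-day window, the reported onset and the committee's discretion. No in-window frequency can be derived from the documents. The hepatic case is of the same kind but secondary, and the SAP omission is housekeeping. The correction is still worth making: the count feeds both Table 6 and a primary endpoint, and investigators should not have to choose between readings.

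**What to change.** Add one sentence after the exemption list in the Synopsis and in Protocol Section 4.1.1.3: *The Grade 3 non-skin irAE exemption does not apply to neurological toxicity, or to events meeting the AST/ALT >3 x ULN with total bilirubin >2 x ULN criterion.* With this in place, two Grade 3 neurological irAEs in three patients count 2/3 however first occurrence is read.

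As housekeeping, have SAP Sections 2.2.4 and 6.3.1.7 cross-refer to the combination DLT definition in Protocol Section 4.1.1.3.

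The cost is wording, plus slightly more events counted as DLTs, so a combination dose is expanded or stopped slightly more often. If a fraction p of patients had such an event and there were no other DLTs, the chance that a level clears would fall from 1 to (1 - p)^3 + 3p(1 - p)^5. That is 0.999 at an assumed p of 1% and 0.906 at an assumed 10%. The loss is material only where these events are common, and there caution is wanted.
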